13.6 Treatment Day Procedures

Prior to sampling, the subjects will be questioned regarding adherence to the qualification criteria.

Subjects will don a disposable undergarment and be examined physically to ensure no evidence of injury, dermatosis, or dermatitis is present in the test areas. One sterile surgical marker will be used per subject. The marker will be used to demarcate a 5" × 5" areas of skin on the right and left sides of the abdomen, adjacent to the navel that appear to be similar in condition. The marker will again be used to demarcate 2" x 5" areas of skin in the inguinal areas that appear to be similar in condition. During treatment day procedures, subjects will wear disposable gloves to guard against contamination of the test sites.

Subjects will be sampled for treatment day baseline microbial populations on randomly assigned sites of the abdominal and inguinal areas on both sides (Appendix 2). The Cylinder Sampling (Cup Scrub) Technique (Section 13.7) will be used for baseline and post-treatment samples.

All product treatments for a subject will be completed on a single day (Treatment Day). The test materials will be applied to the test sites in accordance with the randomization schedule using repeated back-and-forth strokes for 3 minutes on both abdominal and inguinal test sites with a dry time of 1 minute. Detailed instructions on product application are presented in Appendix 1. All test materials will be weighed before and after application and the weights will be recorded. All subjects will have samples collected 10 minutes \pm 30 seconds and 6 hours \pm 30 minutes post product application on both abdomen and inguinal sites. All sampling times will be calculated from the completion of the dry time of each product following application.

Following collection of the last 6 hours \pm 30 minutes post-product application sample of a test site, the remaining test material will be wiped/cleansed from the test site with a mild soap and/or tap water; test sites will be dried with paper towel.

Cylinder Sampling (Scrub Cup) Technique 13.7

Abdomen and Inguinal Samples

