A sterile cylinder with inner diameter of 3.46 cm² will be held firmly onto the test site to be sampled. A 3 mL aliquot of sterile Sampling Solution (SS) will be instilled into the cylinder, and the skin inside the cylinder will be massaged in a sweeping manner for 1 minute with a sterile rubber policeman. The SS will be removed with a sterile pipette and transferred to a sterile test tube. These procedures will be repeated for a second time. The second recovered aliquot will then be pooled in the test tube with the first aliquot, and the samples plated in duplicate using the appropriate media.

Diluting, Plating, and Counting 13.8

Aliquots of the microorganism suspension (100 dilution) will be serially diluted in sterile Butterfield's Phosphate Buffered Water (PBW), as appropriate. Serial dilution and plating will be completed within 30 minutes. Duplicate pour plates will be prepared from appropriate dilutions with Tryptic Soy Agar with product neutralizers (TSA+) and incubated at 30 °C \pm 2 °C for 72 hours \pm 4 hours. Following incubation, plates may be refrigerated for approximately 48 hours prior to counting.

Colonies will be manually counted and data recorded on appropriate data collection forms for each subject.

Blinding 13.9

The Investigational Product and Vehicle Control will be blinded. The Active Control (SAGE) cannot be blinded, due to package labeling of the marketed product. In order to guard against any bias of the study outcome, technicians who participate in product application or sample collection from subjects during treatment day procedures will not participate in the processing of samples. The technicians processing samples and/or counting the resultant plates will be blinded to the study randomization during the data

This Protocol has been approved by the GIRB on 09 [20]

gathering processes. In the event that data and calculations are handled by BSLI staff, the plate counts and calculations will be reviewed and/or approved by separate individuals prior to being entered into a data spreadsheet where product information (unblinding) would occur.

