6.5 Inoculum Assay (Initial population) – Test C

Test Inoculum will be assayed by adding a 0.1 mL aliquot of the inoculum to 5.0 mL of PBS solution (IP), vortexing for at least 3 seconds, and immediately (within 1 minute) pour-plating, in duplicate, 1 mL aliquots of the IP with TSA. This assay will be performed three additional times for a total of four replicates.

The diluted test inoculum suspensions will be allowed to stand for at least 30 minutes, following which, 1 mL aliquots will be pour-plated, in duplicate, with TSA.

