6.7 Neutralizing/Recovery Medium Inhibition Evaluations (In Vitro) – Test B

This phase of the neutralization assay assures that the sterile Sampling Solution (SS), the sampling solution employed in the evaluation, are not inherently toxic to the microorganisms. This assay will be performed in four replicates.

To each of four test tubes containing 5.0 mL of the sampling solution, a 0.1 mL aliquot of the test inoculum will be added. The suspensions will be vortexed for at least 3 seconds and, immediately (within 1 minute), 1 mL aliquots of each replicate will be pour-plated, in duplicate, with Tryptic Soy Agar with product neutralizers (TSA+).

The tubes will be allowed to stand for at least 30 minutes, following which 1 mL aliquots of each replicate will be pour-plated, in duplicate, with TSA+.

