7.0 CALCULATIONS AND DATA HANDLING

Count colonies on plates that have between 25 and 250 colonies per plate. If no plates provide counts in that range, counts from those plates closest to that range will be used for analysis.

The microbial population recovered from each replicate of Test A, Test B, Test C, and Test D will be calculated as follows:

 Log_{10} Average Population = $log_{10}(C_i \times 10^{-D})$

Where:

 C_{i} Average of the plates counted

D Dilution Factor of the plates counted (for example, the dilution =factor is 0 for plating 1.0 mL aliquots and is -1 when plating 0.1

mL aliquots.)

NOTE: The reason that a log₁₀ transformation will be performed on the collected data is to obtain a linear scale. A linear scale, more appropriately a log₁₀ linear scale, is a basic requirement of the statistical models used in this study.

If colonies on one of the plates are uncountable, the count from the remaining plate will be used.

The raw data from sampling of all sites evaluated on a subject will be recorded on data collection forms.

8.0 **STATISTICS**

After calculating the log₁₀ populations recovered from Tests D, B, and A, these will be statistically compared to the Initial Population (Control) using a One-Way Analysis of Variance (ANOVA) with Dunnett Multiple Comparisons with the Control. All statistical calculations will be performed using the 0.05 level of significance for Type I (α) error.

Prior to comparing Phases to the Initial Population (Control), the 30-minute evaluation of the Initial Population should be shown to be statistically equivalent to the "time-zero" Initial Population of the microorganism. Hypotheses are:

 H_0 : Initial Population = Test Phase, or

 H_A : Initial Population \neq Test Phase.

If $p \le 0.05$ for each comparison to the control, H_0 will be rejected and the Test Phase will be considered to be significantly different from the Initial Population. There is potential for low variance of the data, which would result in rejecting H_0 . The difference between the Initial Population and the Test Phase will also be used to confirm significant differences. If the difference is greater than or equal to 0.20, the two tests will be determined to be significantly different. Differences less than 0.20 between the two tests will be determined to be not different.

The Product Efficacy Evaluation is effective if the antimicrobial test product produces a significant reduction in the population of the microorganism.

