The Neutralizing/Recovery Medium Inhibition Evaluations are considered non-inhibitory if all recovered populations are not statistically different from the Initial Population of the microorganism.

The Diluent Broth Inhibition Evaluation is considered non-inhibitory if all recovered populations are not statistically different from the Initial Population of the microorganism.

Neutralization is considered adequate if all recovery populations are not statistically different from the Initial Population (with the exception of Test D). See table below for summary.

Neutralization Test/Phase	Required Results for Acceptance
Test Organism Viability/Initial Population –	30 minute sample cannot be statistically
Test C (IP)	different from 1 minute, or the evaluation
	fails.
Test Material Control/Product Efficacy –	Must be statistically different than Test C at
Test D (Phase I)	the within 1 minute and 30 minutes samples.
Neutralizer Toxicity Evaluation –	
Test B (Phase II)	
Diluent/Recovery Broth Toxicity Evaluation –	Cannot be statistically different at the within 1
Test B (Phase III)	minute or 30 minute samples.
Neutralization Effectiveness Evaluation –	
Test A (Phase IV)	

All values will be compared against the IP. The 30 minute evaluations of any test are used as a time representative to the longest possible wait time of a sample prior to being plated. A comparison will be performed against the FP to ensure the challenge suspension populations were consistent through testing.

The results and all source documents of the neutralization evaluation will be presented as an addenda in the Final Report.

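### Neutralization is judged only against inoculum in PBS on plain TSA, never against its product-free match (Test B), so residual inhibition above the plan's own 0.20 log10 limit can pass if Sampling Solution and TSA+ raise recovery

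*Combined protocol and SAP*

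**What the plan says.** Appendix 3 describes the laboratory conditions in Sections 6.5 to 6.9 and the decision rule in Section 8.0.

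- Test C, the Initial Population, is inoculum in PBS. Section 6.5 specifies "pour-plating, in duplicate, 1 mL aliquots of the IP with TSA", that is, agar without neutralizers.
- Test B (Phase II, Section 6.7) is inoculum in Sampling Solution with no product, plated on TSA+. Phase III (Section 6.8) is the same with the PBW diluent.
- Test A (Section 6.9) is a scrub-cup sample in Sampling Solution taken 10 minutes after product application, then inoculated and plated on TSA+.
- The analysis is a "One-Way Analysis of Variance (ANOVA) with Dunnett Multiple Comparisons with the Control", the control being the Initial Population. A size rule is added: "If the difference is greater than or equal to 0.20, the two tests will be determined to be significantly different". Smaller differences count as no difference.
- The text after the acceptance table repeats that "All values will be compared against the IP". The only other comparisons are Test C at 30 minutes against time zero and a check against the Final Population.

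In the trial, Section 13.6 states that the scrub-cup technique "will be used for baseline and post-treatment samples". Sections 13.7 and 13.8 show that these samples are collected in Sampling Solution, diluted in PBW as needed, and plated on TSA+.

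**The concern.** A log10 reduction is the Treatment Day baseline minus the post-treatment count (Section 15.1). Carried-over product distorts it by the recovery of a product-free sample minus the recovery of a product-bearing sample, both in the trial's fluid and agar. In the validation that difference is B minus A. The plan instead tests A against C and B against C separately, and no trial sample is handled as Test C is.

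Section 2.0 of Appendix 3 sets out exposure to the neutralizing solution alone and to the neutralizing solution plus product, as the means of detecting inhibition. Both arms are run, but Section 8.0 never sets one against the other. If the shift from PBS/TSA to Sampling Solution/TSA+ raises recovery, that gain can hide part of a real loss from unquenched product. At stake is whether a passed validation supports the post-treatment counts behind the 2-log and 3-log responder definitions and the 70% standard.

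**Working it through.** **Design figure.** 8 subjects × 2 sides ÷ (2 products × 2 organisms) = 4 samples per product and organism. This reproduces the plan's figure. The 0.20 margin is stated without derivation.

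**Conditions side by side.**

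| Condition | Fluid | Product residue | Agar |
|---|---|---|---|
| Test C | PBS | no | TSA |
| Test B, Phase II | Sampling Solution | no | TSA+ |
| Test A | Sampling Solution | yes | TSA+ |
| Trial baseline | Sampling Solution, diluted in PBW as needed | no | TSA+ |
| Trial post-treatment | Sampling Solution, diluted in PBW as needed | yes | TSA+ |

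**Bound.** Let a, b, c be the log10 recoveries in Tests A, B and C. Then b − a = (b − c) − (a − c). If each bracket must be smaller than 0.20 in size, the largest b − a that can pass is just under 0.20 + (b − c):

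- b − c near +0.20: just under 0.40 (10^0.40 = 2.51, so about 60% of colonies lost)
- b − c = 0: just under 0.20 (10^0.20 = 1.58, about 37% lost)
- b − c = −0.15: just under 0.05, stricter than comparing A with B

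**Counting error.** 0.1 mL of inoculum at 3.0×10³ to 1.0×10⁴ CFU/mL in 5.1 mL gives 59 to 196 CFU per 1 mL plate. The Poisson SD of a duplicate mean is 0.4343/√(2×59) = 0.040 to 0.4343/√(2×196) = 0.022 log10. The replicate SD is not given; 0.05 to 0.10 is assumed below.

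**Chance of passing.** Simulated with 4 replicates, both times required, the 0.20 rule, and the same offsets throughout. Phase III is not modelled. Ranges run from SD 0.05 to SD 0.10.

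| Offsets from C | True b − a | Plan, 1 product and 1 organism | Plan, 2 products and 2 organisms | A v B alone, 1 product and 1 organism |
|---|---|---|---|---|
| B +0.10, A −0.10 | 0.20 | 99% to 71% | 97% to just under 40% | 25% |
| B +0.15, A −0.15 | 0.30 | 71% to 29% | just under 40% to 3% | under 1% |

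The four-way column is closer to the plan's acceptance rule, which requires all recovery populations to pass. The two times are treated as independent although they come from the same tube. With correlation 0.5, the 25% becomes 33%.

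**Which rule governs.** If p ≤ 0.05 alone decided, a Dunnett critical value near 2.75 with 4 replicates gives a passing limit of 2.75 × SD × √(2/4), about 0.10 at SD 0.05 and 0.19 at SD 0.10. The 0.40 ceiling would then fall. If failure needed both p ≤ 0.05 and a difference of at least 0.20, larger differences could pass once the pooled SD exceeds about 0.10.

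**Where it would act in the trial.** From the Section 13.10 formula, CFU/mL = 10^R × 3.46/6.

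- Groin, baseline 5.50, exactly 3-log reduction: 10^2.50 × 3.46/6 ≈ 182 CFU/mL
- Abdomen, baseline 3.11, exactly 2-log reduction: 10^1.11 × 3.46/6 ≈ 7 CFU/mL
- Groin, baseline 6.5, exactly 3-log reduction: 10^3.50 × 3.46/6 ≈ 1,800 CFU/mL

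The first two would be countable undiluted, where carry-over is greatest. The third would need dilution if the 25 to 250 range of Appendix 3 Section 7.0 were used.

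**Illustrative effect on responders.** Assume normal log reductions with SD 1.2 to 0.8 and one-for-one carry-over. A true 60% reads as Φ(Φ⁻¹(0.60) + shift/SD): 66% to 69% for a shift of 0.199, 69% to 74% for 0.30, and 72% to 77% for 0.398.

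**The case against.** - **The harmful direction is not evidenced.** Reaching 0.40 needs Sampling Solution/TSA+ to recover about 58% more colonies than PBS/TSA. Nothing in the documents suggests this, and the plan's stated worry is the opposite: toxic neutralizers. If B lies below C, the present comparison is the stricter one. This stands, and it makes 0.40 a ceiling and not an estimate. About half of that ceiling comes from the 0.20 margin itself, which an A against B test would keep.
- **Dilution weakens carry-over.** A reader might infer that passed inhibition adds in full to every active-product log reduction. The documents do not support that. Serial dilution in PBW also dilutes residual product on the plate, and at 6 hours the cut-off is the baseline itself, at least 10^5.50 × 3.46/6 ≈ 182,000 CFU/mL in the groin. Inhibition in the tube before dilution would remain, as would the effect on samples plated undiluted.
- **Test B is also only an approximation.** Qualifying baselines are plated after PBW dilution, closer to Phase III. Test A is a wash from alcohol-prepared skin and may carry skin material, whereas Test B is a clean tube. Both points stand. Even so, B shares A's fluid and agar, and C shares neither.
- **The Initial Population may be the prescribed control.** The cited ASTM standard and the facility's procedure are not available here, so it cannot be called a wrong reference. The point does not need that: the product-free contrast is absent whatever the status of C.
- **Replacing C would lose a safeguard.** With B = −0.19 and A = −0.38, A would pass against B. A against C must therefore stay.

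**Conclusion.** The gap is real and limited. Test A is accepted on a comparison that mixes a fluid and agar difference with residual product inhibition, and the contrast that separates them is never made. Inhibition beyond 0.20 log10 can pass only if Sampling Solution/TSA+ recovers more than PBS/TSA. The ceiling is just under 0.40 and assumes that the 0.20 rule decides. With B equal to C nothing is lost.

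A reader might infer that this trial's log reductions are inflated by up to 0.40, or that Test B should replace the Initial Population as the reference. Neither is supported. The actual B minus C is unknown, and carry-over shrinks with dilution. The pass rates and responder figures rest on assumed SDs and assumed offsets. What is supported is adding one contrast that can only tighten control of residual inhibition. Section 10.0 requires the validation to be finished before the clinical phase, so the change belongs there.

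**What to change.** In Appendix 3 Section 8.0 and the acceptance table, add a required comparison of Test A with Test B (Phase II, Sampling Solution on TSA+). Make it for each product and each organism, at matching times (1 minute with 1 minute, 30 minutes with 30 minutes), with the same 0.20 log10 limit. Keep A against C, B against C, and C at 30 minutes against 1 minute as they are. If A fails against C but passes against B, report that failure as a medium or agar effect and not as failed quenching.

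The cost is one added acceptance row. The plates are already planned, so no subjects, samples or staff are added. The downside is a slightly higher chance that the validation fails. There are 2 products × 2 organisms × 2 times = 8 new contrasts. If A and B truly agree and the SD is 0.10, the SD of a difference of 4-replicate means is 0.10 × √(2/4) = 0.071. Each contrast then fails with probability P(|Z| ≥ 0.20/0.071) ≈ 0.005, so the eight together add at most about 4 percentage points. At SD 0.05 the addition is negligible. It is larger if A truly lies below B but within the limit.
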